## **7.6. Clinical Laboratory Tests**

### **7.6.1. Blood Volume**

Total blood sampling volume estimated for this study depends upon subject response:

- Total blood volume for non-responders completing 12 weeks is approximately 113 mls;
- Total blood volume for responders completing 52 weeks is approximately 166 mls;
- Maximum total blood volume estimated for a responder that flares on the last day of the maintenance period and completing 64 weeks is approximately 198 mls.

An additional 5 mls is added to these volumes for adolescents requiring VZV testing.

Further details regarding the collection, processing, storage, and shipping of the blood samples will be provided in the lab manual.

### **7.6.2. Laboratory Tests**

The following laboratory tests will be performed at time points identified in the [Schedule of Activities](#). Unscheduled clinical labs may be obtained at any time during the study to assess any perceived safety concerns at the investigator's discretion.

Sample collection, labeling, storage, and shipping information can be found in the laboratory manual. All laboratory tests with clinically important changes from baseline identified after administration of investigational product will be followed until the value stabilizes.

Subjects must abstain from all food and drink (except water and non-study medications) for an 8-hour overnight fast prior to labs that include the lipid profile panel on Day 1, Week 4, Week 12, Week 52, and EOS for subjects who complete double-blind treatment. For subjects that enter the rescue period, fasting labs are required at Rescue Day 1, Week 4, Week 12, and EOS. All other labs do not require fasting.

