- i. Hematology includes: Hemoglobin, hematocrit, red blood cell count and indices (MCH, MCHC, MCV, RBC Morphology), white blood cells, neutrophils (%), lymphocytes (%), monocytes (%), eosinophils (%), basophils (%), platelets, reticulocyte count, lymphocyte subsets and markers (Total T cells [CD3+], CD4+ T cells [CD3+CD4+], CD8+ T cells [CD3+CD8+], NK cells [CD3- CD16+CD56+], B cells [CD3-CD19 +).
- j. Coagulation panel includes: Activated Partial Thromboplastin Time (APTT), Prothrombin Time/International Normalized Ratio (PT/INR).
- k. Serum chemistry includes: blood urea nitrogen (BUN), serum creatinine, creatine phosphokinase, glucose, Ca++, Na+, K+, Cl, total CO2, aspartate aminotransferase (AST), alanine aminotransferase (ALT), gamma-glutamyl transferase (GGT), total, indirect and direct bilirubin, alkaline phosphatase, lactate dehydrogenase, uric acid, albumin and total protein.
- l. Urinalysis includes: pH, Glucose (qualitative), Protein (qualitative), Blood (qualitative), Ketones, Nitrites, Leukocyte esterase, Microscopy and/or culture (performed as appropriate).
- m. Lipid Panel includes: total cholesterol, low-density lipoprotein (LDL), high-density lipoprotein (HDL), and triglycerides. A minimum of 8-hour fasting is required for lipid profile evaluation at Day 1, Week 4, Week 12, Week 52 and EOS visits.
- n. Serum pregnancy testing at screening is required for women of childbearing potential including adolescents aged 12 years and older regardless of whether they have experienced menarche. Follicle stimulating hormone (FSH) test to be performed at Screening to confirm postmenopausal status in female subjects who have been amenorrheic for at least 12 consecutive months.
- o. Urine pregnancy test must be performed at every site visit prior to dosing with the investigational product for female subjects of childbearing potential including adolescents aged 12 years and older regardless of whether they have experienced menarche.
- 
- q. Subjects testing positive for HIV will be screen-failed.
- r. HBsAb reflex testing will be performed only if HBsAg negative but HbCAb positive. Subjects who are positive for HCVAb and HCV RNA will be screen-failed.
- s. VZV IgG antibody testing is required to confirm eligibility in adolescent subjects who have not received at least one dose of a varicella vaccine.

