  - e. Serum chemistry includes: blood urea nitrogen (BUN), serum creatinine, creatine phosphokinase, glucose, Ca++, Na+, K+, Cl, total CO2, aspartate aminotransferase (AST), alanine aminotransferase (ALT), gamma-glutamyl transferase (GGT), total, indirect and direct bilirubin, alkaline phosphatase, lactate dehydrogenase, uric acid, albumin and total protein.
  - f. Urinalysis includes: pH, Glucose (qualitative), Protein (qualitative), Blood (qualitative), Ketones, Nitrites, Leukocyte esterase, Microscopy and/or culture (performed as appropriate).
- 
- h. Lipid Panel includes: total cholesterol, low-density lipoprotein (LDL), high-density lipoprotein (HDL), and triglycerides. A minimum of 8-hour fasting is required for lipid profile evaluation at the following Rescue Visits: Day 1, Week 4, Week 12 and EOS visits.
  - i. Urine pregnancy test must be performed at every site visit prior to dosing with the investigational product for female subjects of childbearing potential including adolescents aged 12 years and older regardless of whether they have experienced menarche.
  - j. Subjects should take the medication from study Days 1 to 85 of the rescue treatment. Subjects will be encouraged to take the medication in the morning whenever possible; however, at study visit days, subjects are to be instructed to refrain from dosing at home and are to take the dose in the clinic.

- k. Subjects who complete EOT will be assessed for eligibility for participation in long-term extension study B7451015 as noted in [Section 6.5.7](#).
- l. Pruritus Numerical Rating Scale (NRS) will be assessed using an eDiary, and will be collected daily in the eDiary from Study Days 1-15 during the rescue treatment and then only on study visit days at the investigative site thereafter. PSAAD will be completed daily (in selected countries) in the eDiary from Day 1 through the End of Study (EOS) visit during rescue treatment. At every visit, the study coordinator will review the eDiary for completeness and counsel the subject on how to complete the items in the daily eDiary, if needed.
- m. DLQI will be completed by adult subjects only. Adolescents 12-17 years of age will complete the CDLQI instead.

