#### **4.4. Lifestyle Requirements**

In order to participate in the study, subjects must be aware of the following lifestyle guidelines and restrictions that apply during and after the treatment period.

- On study visit days: Day 1, Weeks 4, 12, 52 and End of Study (EOS) and corresponding visits if a subject enters the rescue treatment period, subjects must comply with fasting requirement for at least 8 hours prior to the visit. Water and permitted non-study medications are allowed (see [Section 5.9.1](#)).
- On study visit days, subjects must not smoke or ingest caffeine during the 30 minutes prior to blood pressure and heart rate measurements.
- On study visit days, subjects must not take the dose of investigational product until instructed to do so by the investigator or designated study site staff.

- On study visit days, showering or bathing is permitted prior to attending the study visit, but subjects must not moisturize or apply emollient. Non-medicated emollient is allowed after the visit. Discontinue and avoid using certain medications and treatments ([Section 4.2](#), [Section 5.9.2](#), and [Appendix 3](#)).
- Agree to use one highly effective method of contraception (as specified in [Section 4.4.1](#), as applicable).

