### **5.2. Rescue Treatment**

Subjects will be instructed to contact the site if they experience a significant worsening of their atopic dermatitis, such as a recurrence of pruritus, during the double-blind treatment period. Site staff will determine if the subject should return to the site for an unscheduled (see [Section 6.5.1](#)) or regularly scheduled visit (see [Section 6.3](#)). Subject will be reminded not to take study drug on the day of the site visit. At the visit (regular or unplanned) the subject will be assessed for flare, defined as a loss of at least 50% of the EASI response at Week 12 and an IGA of 2 or higher. Subjects who meet the definition of flare are to receive rescue treatment that day and enter an open-label rescue period during which they receive 12-weeks of 200 mg PF-04965842 QD with concomitant topical therapy per SOC. See [Section 5.2.1](#) for guidance on topical therapies.

After completing the rescue period, subjects are allowed to enter the LTE study B7451015, if eligible. If a subject discontinues prematurely or is not eligible or willing to participate in B7451015, then the subject enters the 4-week, untreated follow-up safety period. Refer to [Schedule of Activities for Rescue Treatment](#).

Subjects not meeting the definition of flare will continue on their blinded treatment. Physicians may continue to clinically evaluate for flare using the EASI and IGA assessments at their discretion.

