6.7. Safety Summaries and Analyses

Safety analysis will be based on the SAF analysis sets (see [Section 4.3](#)). The SAF-OL analysis set will be used to summarize the safety experience for all subjects during the first 12 weeks of open label treatment with PF-04965842 200 mg QD using the Study Baseline (see [Section 3.4](#)). The SAF-RA analysis set will be used to summarize the safety experience for all randomized subjects using the Randomization Baseline. Subjects who report a protocol-defined flare and get rescue treatment will be censored at the day before the first day of rescue in this analysis. All subjects will be classified according to the actual treatment regimen they received. The SAF-RE analysis set will be used to summarize the safety experience for the subjects who receive rescue treatment using the Rescue Baseline. Study Baseline will be used for all displays of results meeting lab abnormality criteria, throughout the subject's study experience.

All clinical AEs, SAEs, treatment-emergent signs and symptoms (TEAEs), withdrawal due to AEs, ECGs, vital signs and safety laboratory data will be summarized to evaluate the safety of subjects.

Safety data will be presented in tabular and/or graphical format and summarized descriptively, where appropriate. All safety endpoints will be listed and summarized in accordance with Pfizer Standards. Categorical outcomes (eg, AEs) will be summarized by subject counts and percentage. Continuous outcome (eg, blood pressure, pulse rate, etc.) will be summarized using N, mean, median, standard deviation, etc. Change from baseline in laboratory data, ECGs and vital signs will also be summarized. Subject listings will be produced for these safety endpoints accordingly. Separate summaries will be displayed for adjudicated data on cardiovascular (CV), malignancy, opportunistic infection, histopathologic and hepatic events.

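### For flares found at Weeks 16, 28 or 40, and possibly at unplanned visits, the Rescue Day 1 lipid sample may be non-fasting, although the protocol requires a fast and the SAP uses that sample as the Rescue Baseline.

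*Protocol*

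**What the plan says.** **Fasting in the rescue period.** A footnote to the rescue schedule states: "A minimum of 8-hour fasting is required for lipid profile evaluation at the following Rescue Visits: Day 1, Week 4, Week 12 and EOS visits". The opening of Protocol Section 6 repeats the Rescue Day 1 fast. Section 7.6.2 says of subjects who enter rescue that "fasting labs are required at Rescue Day 1, Week 4, Week 12, and EOS. All other labs do not require fasting". Section 6.5.1 (flare at an unplanned visit) asks for fasted samples with a lipid profile.

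**Fasting before rescue.** The run-in and blinded schedule states: "A minimum of 8-hour fasting is required for lipid profile evaluation at Day 1, Week 4, Week 12, Week 52 and EOS visits". Weeks 16, 28 and 40 are not listed, and Sections 6.3.2 to 6.3.4 specify neither a fast nor a lipid profile there. Section 4.4 gives subjects the rule as "Day 1, Weeks 4, 12, 52 and End of Study (EOS) and corresponding visits if a subject enters the rescue treatment period".

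**Start of rescue.** Flare is assessed at Weeks 16, 28, 40 and 52 and at unplanned visits. Section 5.2 says: "Subjects who meet the definition of flare are to receive rescue treatment that day". For a subject who has called the site about worsening, the preparation stated there is: "Subject will be reminded not to take study drug on the day of the site visit".

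**Analysis.** SAP 3.4 defines Rescue Baseline as the last value between the last blinded dose and the first rescue dosing day, whatever the fasting status. SAP 3.5.2 lists cholesterol, LDL, HDL and triglycerides among the laboratory parameters. SAP 6.7 uses SAF-RE to summarise the "safety experience for the subjects who receive rescue treatment using the Rescue Baseline", and SAP 6.7.2 applies this to laboratory change up to the end of rescue.

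**The concern.** The fast at Rescue Day 1 has to be prepared for hours ahead, but whether a visit becomes Rescue Day 1 is known only once EASI and IGA have been scored at that visit. The rule in Section 4.4 presumes that the subject already knows rescue is starting. A subject who follows the plan exactly can arrive fed at Week 16, meet the flare definition, start rescue that day and provide a fed lipid sample that the protocol says must be fasted.

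Rescue Weeks 4 and 12 are planned fasting visits. The change from Rescue Baseline can therefore compare fed with fasted values, an error that runs in one direction. For a subject who flares before Week 52, the Rescue Day 1 sample is also the only scheduled lipid value between Week 12 and Rescue Week 4. It is thus the only one that reflects blinded treatment before open-label 200 mg resumes. Once taken fed, it cannot be recovered.

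**Working it through.** The plan gives no figure to reproduce, so the check sets the visit lists side by side.

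**Step 1: routes into rescue against fasting status.**

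| Route into rescue | Fast called for before flare is known? | Agrees with the Rescue Day 1 fast? |
|---|---|---|
| Week 16 (6.3.2) | No | Conflict |
| Week 28 (6.3.3) | No | Conflict |
| Week 40 (6.3.4) | No | Conflict |
| Week 52 (6.3.5) | Yes, with lipid profile | Consistent |
| Unplanned visit (6.5.1) | Fasted sample required, but no fasting reminder in 5.2 | Required, not assured |

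Three of five routes conflict, one is consistent and one is uncertain. These are counts of routes, not of subjects. The documents do not say how flares divide among the visits.

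**Step 2: could a fasted baseline be obtained another way?** Rescue Visit 1 has a window of ±3 days, but a fasted sample taken on a day after the first rescue dose falls outside the SAP's Rescue Baseline. The previous scheduled lipid panel is Week 12. It was drawn on open-label 200 mg before any blinded dose, so it also falls outside that definition. Morning visits are preferred in Section 6 but not required, so they make a fast possible without securing it.

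**Step 3: direction and form of the error.** Let f be the share of rescue subjects whose baseline is fed. Let d be their mean fed-minus-fasted difference. For absolute change, which is the change SAP 6.7.2 plans:

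expected observed mean change = true mean change − f × d.

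If feeding raises the analyte (d > 0; assumed here, and mainly relevant to triglycerides), a rise is understated. Expressed as percent change with no true change, and with D the proportional rise after food, the error is −f × D/(1 + D).

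**Step 4: size.** The documents give neither f nor d nor D. Purely to show how the expression scales, under assumed values:

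- f = 0.5, D = 15%: 0.5 × 0.15/1.15 = 0.065, about 6.5 percentage points.
- f = 0.9, D = 30%: 0.9 × 0.30/1.30 = 0.208, about 21 percentage points.

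This range follows entirely from the assumed inputs and is not an estimate for this trial.

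**The case against.** The strongest reply is that the protocol does require the fast. Section 4.4, the opening of Section 6, Section 6.5.1, Section 7.6.2 and the schedule footnote all say so. At an unplanned visit the subject has normally contacted the site first, so staff can add the instruction. Some subjects will arrive fasted in the morning anyway. Fasting status may already be recorded under the laboratory manual, which is not available here. All of this stands for unplanned visits, where the gap is a missing reminder. It does not help at Weeks 16, 28 and 40, where a compliant subject has no reason to fast. Section 6.5 repeats the rescue rule without saying that treatment starts the same day, but it does not override Section 5.2, which does.

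The second reply is that little depends on this summary, and that is largely right. SAF-RE safety data are descriptive and, under SAP Section 6, are not displayed by treatment group. Displays of laboratory abnormalities use Study Baseline, which is a scheduled fasting visit (SAP 6.7). Absolute values on rescue are shown as well.

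Three stronger readings are tempting, and the documents do not support them:

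- **That rescue lipid change is measured from a non-fasting baseline throughout, or that subjects are told not to fast before unplanned visits.** Week 52 is a fasting visit, Section 6.5.1 asks for fasted samples, and no section tells those subjects that a fast is unnecessary.
- **That the trial could miss a lipid rise on 200 mg.** Fasted lipids are taken at Day 1 and Weeks 4 and 12 of open-label 200 mg and summarised from Study Baseline, and the randomised 200 mg arm has a fasted panel at Week 52.
- **That many Rescue Day 1 samples will be protocol deviations.** Without the split of flares by visit, no count can be given.

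**Conclusion.** The point holds in a limited form. For flares found at Week 16, 28 or 40, the same-day start of rescue cannot be reconciled with an assured 8-hour fast at Rescue Day 1. For unplanned visits the fast is required but not prepared for. The SAP has no rule for a Rescue Baseline lipid value taken fed.

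The consequence is that SAF-RE lipid change may be understated, mainly for triglycerides, for an unknown share of subjects. This rests on two assumptions: that some of these subjects attend fed, and that feeding raises the value. A reader might multiply a guessed share by a guessed post-meal rise and report the product as the bias in percent change. The documents supply neither input, the product is the wrong form for percent change, and percent change is not what SAP 6.7.2 plans for laboratory data. The size should be left unstated.

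The primary and key secondary endpoints, the error rate, power and sample size are untouched. This is a minor but inexpensive correction to a planned safety summary.

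**What to change.** **Protocol.** Reconcile Sections 4.4, 5.2, 6 (opening), 6.3.2 to 6.3.4, 6.5.1 and 7.6.2, with the matching schedule footnotes. Extend the 8-hour fast, with water allowed, to Weeks 16, 28 and 40, and add it to the existing reminder in 5.2 for visits prompted by worsening. This concerns sample preparation only; it leaves dosing, the flare definition and the timing of rescue as they are.

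**Data collection.** Record fasting status with each lipid sample, if the laboratory manual or CRF does not already capture it.

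**SAP 3.4 and 6.7.2.** Summarise SAF-RE lipid change from fasted Rescue Baselines only. Flag or list subjects with non-fasted baselines separately, and show change from Study Baseline as context. Do not substitute the Week 12 value. It follows 12 weeks of open-label 200 mg and precedes blinded dosing, so for subjects randomised to placebo or 100 mg it would compare two values on 200 mg and could itself mask a rise on rescue.

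**Cost.** Amendment and SAP wording, possibly one data field, and a fast before up to three more visits, which are preferably held in the morning. No extra sample is drawn. If the visit instructions cannot be changed, the fasting-status record and the SAP rule are still worth having.

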### Laboratory Tests

Hematology	Serum Chemistry	Urinalysis	Other
Hemoglobin	BUN and Creatinine	pH	HIV a
Hematocrit	Creatine Phosphokinase	Glucose (qual)	HBsAg a
RBC indices	Glucose	Protein (qual)	HBcAb a
MCH	Na + , K + , Cl  , Ca ++	Blood (qual)	HBsAb b
MCHC	Total CO 2 (Bicarbonate)	Ketones	HCVAb a
MCV	AST, ALT	Nitrites	HCV RNA b
RBC Morphology	GGT	Leukocyte esterase	VZV IgG Ab e
RBC count	Total, Indirect & Direct Bilirubin	Microscopy and/or	Serum FSH
Reticulocyte count	Alkaline phosphatase	culture d	(post-menopausal women)
Platelet count	Lactate dehydrogenase		or Pregnancy Test a, c
WBC count with differential	Uric acid		Urine pregnancy test c
Total neutrophils (% Abs)	Albumin		QFT-G or PPD (if applicable) e
Eosinophils (% Abs)	Total protein		HSV-1, HSV-2, VZV
Monocytes (% Abs)	Lipid Profile Panel f		Lymphocyte Subsets
Basophils (% Abs)	Total cholesterol		(Lymphocyte Markers)
Lymphocytes (% Abs)	LDL		Total T cells (CD3+)
Coagulation Panel	HDL		CD4+ T cells (CD3+CD4+)
Activated Partial	Triglycerides		CD8+ T cells (CD3+CD8+)
Thromboplastin Time			NK cells
Prothrombin			(CD3-CD16+CD56+)
Time/International			B cells (CD3-CD19+)
Normalized Ratio			HBV DNA h
(PT/INR)			

- a At Screening only. HIV testing will be performed for all subjects.
- b HBsAb reflex testing only if HBsAg negative but HBcAb positive. HCV RNA is reflex testing only if HCVAb is positive.
- c Pregnancy testing for women of childbearing potential including adolescents aged 12 years and older regardless of whether they have experienced menarche; serum FSH for women who have been amenorrheic for at least 12 consecutive months.
- d Microscopy with culture performed as appropriate.
- e PPD results should be read within 48 to 72 hours.
- f Lipid Profile Panel requires at least an 8 hour fast. Lipid profile panel will be completed at Day 1, Week 4, Week 12, Week 52, and EOS, and will include total cholesterol, LDL, HDL, and triglycerides. For subjects receiving rescue therapy, a lipid profile will be completed at rescue Day 1, Weeks 4, 12 and EOS.
- g Only for adolescents who do not have documentation of at least one dose of varicella vaccine.
- h For China and Taiwan only: Subjects who are HBsAg negative, HBcAb positive, and HBsAb positive at Screening will have reflex testing for HBV DNA. Subjects who have HBV DNA above the lower limit of quantification (LLQ) will be excluded. Subjects who are HBV DNA negative or below LLQ may enroll but will have HBV DNA testing repeated at Weeks 12, 28, 40, 52, Rescue Week 12, and early termination from study during any treatment period.

Clinically significant abnormal findings should be recorded as AEs. Abnormal test results determined to be caused from laboratory error should not be reported as AEs. Clinically significant laboratory findings at the final assessment should be followed to resolution or until determined by the investigator to be stabilized. Repeat tests may be indicated to establish this. Subjects who are positive for HIV will be screen-failed. Refer to [Appendix 4](#) for Guidelines on Monitoring and Discontinuation.

### 7.6.2.1. Hepatitis Testing

**Hepatitis B testing:** HB surface antigen (HBsAg), HB core antibody (HBcAb), HB surface antibody (HBsAb).

#### *Interpretation of Hepatitis B Testing Results:*

- HBsAg negative and HBcAb negative: Subject is eligible for the study;
- HBsAg positive and HBcAb negative: Subject is excluded from study participation;
- HBsAg negative and HBcAb positive and HBsAb positive: Subject is eligible for study;
- HBsAg negative and HBcAb positive and HBsAb negative: Subject is excluded from study participation.

**For China and Taiwan only:** Subjects who are HBsAg negative, HBcAb positive, and HBsAb positive at Screening will have reflex testing for HBV DNA. Subjects who have HBV DNA above the LLQ will be excluded. Subjects who are HBV DNA negative or below LLQ may enroll but will have HBV DNA testing repeated at Weeks 12, 28, 40, 52, Rescue Week 12, and early termination from study during any treatment period.

A single positive HBV DNA test result above the LLQ for a subject requires immediate and permanent discontinuation from treatment, and the Medical Monitor (or designee) must be notified. The subject must be scheduled for an End of Treatment visit/Early Termination visit, enters the end of treatment follow up period, and must be scheduled for an End of Study visit. No further scheduled HBV DNA tests will be required for a subject once a result above the LLQ is established for that subject during any study in the program. Follow up by the investigator is required as detailed in [Section 8.1.4.1](#).

**Hepatitis C testing:** Hepatitis C Antibody (HCV Ab), Hepatitis C Viral RNA (HCV RNA for confirmation of positive HCV Ab result).

